5.6.5 Early study termination by the sponsor

The study can be terminated by Novartis at any time for any reason. This may include reasons related to the benefit risk assessment of participating in the study, practical reasons, or for regulatory or medical reasons (including slow enrolment). Should this be necessary, the subject must be seen as soon as possible and treated as a prematurely discontinued subject. The investigator may be informed of additional procedures to be followed in order to ensure that adequate consideration is given to the protection of the subject's interests. The investigator will be responsible for informing the Institutional Review Board/Independent Ethics Committee (IRBs/IECs) of the early termination of the trial.

6 Visit schedule and assessments

[Table 6-1](#) and [Table 6-2](#) list all of the assessments and indicate with an “X” when the visits are performed.

Subjects must be seen for all visits on the designated day, or as close to it as possible. Missed or rescheduled visits will not lead to automatic discontinuation.

Screening will be flexible in duration based on the time required to be evaluated for eligibility. Sufficient time is allowed for potential medication washout, in addition to all other assessments indicated in [Table 6-1](#). Upon confirmation that all inclusion and exclusion criteria have been met, the subject may be randomized. The full 10-week screening window is not required.

Screening will consist of two consecutive visits. During Screening Visit 1 (SV1), initial assessments will be performed as outlined in [Table 6-1](#), including the collection of hsCRP central laboratory test and SI joint X-rays. It is recommended that the subject should not proceed to Screening Visit 2 (SV2) until confirmation of sacroiliitis per the Modified NY AS Criteria grading from the centrally read SI joint X-rays ([Appendix 3](#)). One retest of the hsCRP lab result may be performed during the screening period.

While the full screening window available is up to 10 weeks, SV2 should occur within the 4 weeks prior to randomization.

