Cardiovascular medical history		X																													
Serum pregnancy test		X																													
Chest X-ray or MRI ⁷		S																													
Hepatitis B, C or HIV serology (only in countries where required)**		S																													
Smoking history			X																												
Physical Exam		S	S			S				S		S					S									S					S

Period	Screening			Treatment																												
	SV1 -10 to -4	SV2 -4 to BSL	BSL	1	2	3	4	6	8	10	12	14	16	18	20	22	24	26	28	30	32	34	36	38	40	42	44	46	48	50	52	
Height		X																														
Weight		X	X										X																			X
Vital signs		X	X				X				X	X					X									X						X
ECG			X																													
HLA-B27			X																													
Lipids ⁹			X																													X
Hematology, blood chemistry		X	X				X				X	X					X									X						X
Urine pregnancy test			X				X				X	X					X									X						X
Randomization via IRT			X																													
Administration of AIN457 150 mg or 300 mg s.c. study treatment			X	X	X	X	X		X		X		X		X		X		X		X		X		X		X		X		X	
Administration of GP2017 40 mg s.c. study treatment			X	X		X	X	X	X	X	X	X	X	X	X	X	X	X	X	X	X	X	X	X	X	X	X	X	X	X	X	X
MRI ¹⁰ (spine and SI joints)			X																													
BASDAI			X																													
BASFI			X																													
Patient's global assessment of disease activity (PADA VAS)			X																													
Patient's assessment of back pain intensity (PAP VAS)			X																													

Period	Screening			Treatment																												
	SV1 -10 to -4	SV2 -4 to BSL	BSL	1	2	3	4	6	8	10	12	14	16	18	20	22	24	26	28	30	32	34	36	38	40	42	44	46	48	50	52	
Week																																
Concomitant medication/ non-drug therapy	X	X		Updated as necessary																												
Adverse events/ SAEs ¹¹				Updated as necessary																												

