
S To be recorded in source document but not in CRF
 
Greyed visits are visits with at-home dosing, optional for on-site dosing
 
The BSL visit and randomization is Day 1
 
1 Eligibility and relevant medical history assessments are conducted at SV1, SV2 and BSL.
 
2 SI joint and spinal X-ray image acquisition must follow the vendor's Image Acquisition Guidelines. An SI joint X-ray taken within 3 months prior to SV1 may be utilized. The SI joint X-ray will be centrally read for eligibility.
 
3 Spinal X-rays (cervical + thoraco-lumbar) to be collected during the screening period to confirm eligibility for subjects with CRP < 5 mg/L. Subjects with CRP ≥ 5 mg/L and confirmed study eligibility should obtain the spinal X-rays at BSL.
 
4 Re-screening subjects may utilize previous X-rays if taken within the past 3 months according to the imaging criteria.
 
5 The PPD skin test can be performed at any time during the screening period, but it must be read within 72 hours and before randomization.
 
6 AS disease assessment includes: AS disease background, Modified New York criteria for AS and targeted medical history events related to AS.
 
7 A chest X-ray or MRI is required if it was not performed and evaluated within 3 months prior to screening. The X-ray should be performed after it is certain the subject meets inclusion/exclusion criteria in order to minimize unnecessary exposure to radiation. The X-ray may be replaced by an MRI assessment.
 
9 Sample must be obtained fasting.
 
10 MRI only performed in a sub-population of subjects at selected sites. All subjects at the selected MRI site should be considered for the MRI assessment.
 
11 AEs / SAEs occurring after the subject has signed the informed consent must be captured on the appropriate CRF.
 
For all subjects who discontinue from the study, the investigator should ensure that the subject completes the end of treatment visit (Week 104 visit assessments) 4 weeks after last study treatment of secukinumab or 2 weeks after last study treatment of GP2017, and also returns for the final follow-up visits, F112 and F120. Every attempt should be made to obtain the scheduled X-ray and MRI images at the final visit, unless the last X-ray and/or MRI were taken within 12 weeks before discontinuation.
 
** Hepatitis B and/or hepatitis C and/or HIV serology testing to be performed at local site during screening period, only if required per local medical practice or local regulations prior to initiation of therapy. These assessments will be documented in source records only and will not be entered into the CRF.
																																

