6.5.9 Pregnancy and assessments of fertility

All pre-menopausal women who are not surgically sterile will have a serum β -hCG test (serum pregnancy test) performed at the screening visit, and local urine pregnancy tests as indicated in [Table 6-1](#) and [Table 6-2](#). A positive urine pregnancy test requires immediate interruption of study drug until serum β -hCG is performed and found to be negative. Additional pregnancy testing might be performed if requested by local requirements.

Secukinumab and GP2017 should not be given to pregnant women; therefore effective method of birth control must be used for women of child-bearing potential (see exclusion criteria definitions, [Section 4.2](#)).

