7.6 Pregnancy reporting

All pre-menopausal women who are not surgically sterile will have a urine pregnancy test. A positive urine pregnancy test requires immediate interruption of study drug until serum β -hCG is performed and found to be negative.

To ensure subject safety, each pregnancy occurring after signing the informed consent must be reported to Novartis/CRO within 24 hours of learning of its occurrence. The pregnancy should be followed up to determine outcome, including spontaneous or voluntary termination, details of the birth, and the presence or absence of any birth defects, congenital abnormalities, or maternal and/or newborn complications. The study drug must be discontinued, though the subject may stay in the study, if she wishes to do so. All assessments that are considered as a risk during pregnancy must not be performed. The subject may continue all other protocol assessments.

Pregnancy must be recorded on the Pharmacovigilance Pregnancy Form and reported by the investigator to the local Novartis Drug Safety and Epidemiology Department. Pregnancy follow-up should be recorded on the same form and should include an assessment of the possible relationship to the study treatment. Any SAE experienced during the pregnancy and unrelated to the pregnancy must be reported on a SAE form.

8 Data review and database management

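### A new pelvic (SI joint) X-ray is scheduled at SV1, but the first scheduled pregnancy test comes at SV2

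*Protocol*

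**What the plan says.** Protocol Section 6 describes two consecutive screening visits. The SV1 assessments are listed as "including the collection of hsCRP central laboratory test and SI joint X-rays", and Table 6-1 agrees: its only mark for the SI joint film during screening is at SV1. Section 6.4.1 specifies the view as antero-posterior pelvis. On sequence, Section 6 states "It is recommended that the subject should not proceed to Screening Visit 2 (SV2) until confirmation of sacroiliitis" from the centrally read film, and adds: "While the full screening window available is up to 10 weeks, SV2 should occur within the 4 weeks prior to randomization".

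The row "Serum pregnancy test" in Table 6-1 is marked at SV2 only, and the first urine test is at BSL. Section 6.5.9 is less specific. It has the serum test "performed at the screening visit, and local urine pregnancy tests as indicated in" the two schedule tables, without saying which screening visit is meant. It also allows for more: "Additional pregnancy testing might be performed if requested by local requirements".

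Two other provisions matter. Table 6-1 footnote 7, on the chest X-ray, says "The X-ray should be performed after it is certain the subject meets inclusion/exclusion criteria in order to minimize unnecessary exposure to radiation". Section 7.6, on pregnancy, says "All assessments that are considered as a risk during pregnancy must not be performed".

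**The concern.** In the recommended flow the pelvic film comes first, the central read second and the pregnancy test third. Nothing in the protocol requires a test before the film.

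Section 6.4.6 says the spinal and SI X-ray exposure is not needed for the subject's care. The Section 7.6 rule can work only once a pregnancy is known, and at SV1 the schedule has not yet looked for one. Footnote 7 shows that the sponsor accepted the principle of limiting avoidable radiation at screening, but applied it to the chest film only.

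The same gap can arise for the screening spinal film in subjects with hsCRP below 5 mg/L (inclusion criterion 7 and Table 6-1 footnote 3). That film includes a thoraco-lumbar view and may be taken before SV2.

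What is at stake is patient safety in the ordering of procedures, not the statistical analysis.

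**Working it through.** There is no sample-size or power figure to reproduce. The check sets the X-ray schedule beside the pregnancy-test schedule and does simple date arithmetic.

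**1. X-rays and tests by visit (Tables 6-1 and 6-2)**

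| Visit | X-ray | Pregnancy test at the same visit |
|---|---|---|
| SV1 | SI joints; possibly spine if hsCRP < 5 mg/L | none |
| SV2 | chest, if needed | serum |
| BSL | spine | urine |
| Week 104 | SI joints and spine | urine |

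SV1 is the only X-ray visit without a scheduled test. This suggests an oversight in the table, not a deliberate choice.

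**2. Gap from film to first scheduled test**

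Table 6-1 gives SV1 as weeks -10 to -4 and SV2 as week -4 to BSL.
- Longest: SV1 at week -10 and SV2 just before BSL, so about 10 weeks = 10 × 7 = 70 days.
- Shortest: both visits at week -4, so 0 weeks.

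This describes the schedule and does not measure harm. Whether a pregnancy is exposed depends on the day of the film, not on how much later the test falls.

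**3. Scheduled tests for a woman who completes the study**

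Counting marks: 1 serum (SV2) + 7 urine (Table 6-1, BSL to Week 52) + 6 urine (Table 6-2, Week 64 to F120) = 14. Marks before the SV1 film: 0. Some treatment-week marks in the copy of Table 6-1 available to me are out of column alignment, so the count relies on the number of marks. The SV2 position of the serum test is supported by the neighbouring rows.

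**4. Subjects who may never be tested**

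Section 4 plans 1,116 screened and 837 randomized: 1,116 - 837 = 279 screen failures, and 279 / 1,116 = 25%. Those who fail at the SI read may stop before SV2 and so have the film without any scheduled test. The documents do not say how many of the 279 fail at that step, or how many are pre-menopausal women who had a new film.

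**5. Do the existing provisions close the gap?**

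- *Eligibility review at SV1.* Inclusion criterion 2 requires female patients to be non-pregnant, but exclusion criterion 9 defines pregnancy as confirmed by an hCG laboratory test. None is scheduled by then, so the review finds only a known pregnancy.
- *Film reuse.* Footnote 2 allows an SI film from the 3 months before SV1, and footnote 4 allows earlier films at re-screening. These reduce the number of new films but do not protect a woman who has one.
- *Pill stability.* Exclusion criterion 10 requires 3 months on the same pill before study drug. It applies to pill users only, and its reference point is first dose, not the film.
- *Local requirements.* Section 6.5.9 permits extra tests but does not require them. Practice could differ across the approximately 200 centers.
- *Vendor guidelines.* Footnote 2 makes the imaging vendor's acquisition guidelines binding. They are not among the documents, so a pre-film check there can be neither confirmed nor excluded.

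**6. Dose**

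Section 6.4.6 gives about 3.4 mSv a year for all films combined and calls the risk minimal. It gives no pelvic or fetal dose, so the risk to a pregnancy cannot be worked out from the documents.

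**The case against.** The strongest reply is that the change cannot protect anyone in this trial. The Amendment 2 rationale states that enrolment is complete and all subjects have passed Week 52, so every screening film has been taken. The remaining scheduled films, at Week 104, share a visit with a urine test. That stands: the benefit is to the design text and to any later protocol that copies this schedule.

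Second, the vendor's guidelines, site qualification by the imaging lab or local radiology rules may already require a check before a pelvic film. That is possible and limits what can be said about practice. It does not alter what the protocol itself requires, and a protection this basic belongs in the protocol.

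Third, the comparison with footnote 7 is imperfect. The SI film is itself an eligibility test under inclusion criterion 3, so it cannot wait until eligibility is certain, and reading it first spares those who fail the read further screening procedures. That is correct. It is a reason to keep the film at SV1, but a urine test can still precede it.

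Fourth, Section 7.6 concerns reported pregnancies and is not a pre-imaging rule. This is also fair. The SV1 order does not breach Section 7.6; the point is only that its protection cannot reach an unrecognised pregnancy.

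Finally, the 10-week gap, the 14 tests and the 279 screen failures are not counts of harm. Agreed. Section 6 says the full 10-week window is not required, and the conclusion does not depend on any of the three figures.

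**Conclusion.** The point holds. Under the protocol's own schedule, a new research-only pelvic film is taken at SV1 with no pregnancy test scheduled before it, and the first scheduled test follows 0 to about 10 weeks later. Other provisions narrow this gap without closing it.

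The expected number of exposed pregnancies is probably small and cannot be derived from the documents. The conclusion rests on the SV1 and SV2 positions in Table 6-1, on a new film being taken, and on no pre-film check being imposed by documents outside the protocol. It is an inexpensive improvement that should be made, but it does not threaten the trial's validity: endpoints, power and alpha are unaffected.

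**What to change.** 1. **Table 6-1:** keep the serum test at SV2 and the urine test at BSL. Add a local urine pregnancy test at SV1, before any new film, for the women covered by Section 6.5.9 (pre-menopausal and not surgically sterile).
2. **Section 6, after the SV1 assessments, add:** *For pre-menopausal women who are not surgically sterile, a negative pregnancy test is required on the day of, or within 3 days before, any new SI joint or spinal X-ray taken during screening or at BSL. If the urine test is positive, the X-ray is withheld until a serum hCG test is negative.* The 3-day limit is a proposed value, not one taken from the documents.
3. **Section 6.5.9:** name SV2 as the visit for the serum test, and add the local urine test at SV1 before any new X-ray.

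The cost is one table mark, two sentences and one edit. Each woman concerned has one more local urine test (15 scheduled tests instead of 14 for a completer), repeated if a screening spinal film is taken on a later day outside the 3-day limit. The share of such women is not given. As a scale, each 10% of those screened would mean 1,116 × 0.10 = about 112 extra tests. Local urine tests are already used in the trial, so no new procedure is needed.

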6.1 Information to be collected on screening failures

Subjects who discontinue from the study prior to randomization are considered screen failures.

If a subject discontinues before entering the partially-blinded treatment period at baseline, the IRT system must be notified within 2 days and the reason for not being randomized will be entered on the appropriate screening phase CRF. In addition, only the CRFs related to the following assessments should be completed: demography, informed consent, re-screening and inclusion/exclusion. The CRF for adverse events (AEs) should be completed for any Serious Adverse Events (SAEs) that occurred during the screening period. Adverse events that are not SAEs will be followed by the investigator and collected only in the source data.

All subjects who have signed informed consent and are randomized into the Treatment Period of the study will have all AEs **occurring after informed consent is signed** recorded on the CRF capturing AEs, and SAEs if applicable, i.e. when SAE criteria are met.

Investigators will have the discretion to record abnormal test findings on the medical history CRF whenever in their judgement, the test abnormality occurred prior to the informed consent signature.

6.2 Subject demographics/other baseline characteristics

Subject demographic and baseline characteristic data to be collected on all subjects and to be recorded in the CRF include:

- Age, sex, race, ethnicity
- Relevant AS and general medical history/current medical condition data until the start of investigational treatment: targeted medical history events related to AS, such as the history of extra-axial involvement (uveitis, psoriasis, inflammatory bowel disease, dactylitis, enthesitis, peripheral arthritis), number of previous DMARDs used, date of diagnosis of AS, previous AS therapies, functional status class according to the New York criteria, cardiovascular medical history and smoking history

Where possible, diagnoses and not symptoms will be recorded.

Investigators will have the discretion to record abnormal test findings on the CRF capturing medical history whenever in their judgment, the test abnormality occurred prior to the informed consent signature.

6.3 Treatment exposure and compliance

All dates and times of study treatment administration will be recorded on the appropriate CRF.

Drugs administered prior to start of treatment and other drugs/procedures continuing or started during the study treatment period will be entered in the appropriate CRF.

Compliance is expected to be 100%, unless temporary interruption is needed for safety reasons as described in [Section 5.5.5](#). Compliance will be assessed by a field monitor using information provided by the subject and the authorized site personnel. All study treatment dispensed and returned must be recorded in the Drug Accountability Log.

6.4 Efficacy

- X-ray of the cervical, thoracic and lumbar spine assessed by modified Stoke Ankylosing Spondylitis Spinal Score (mSASSS)
- X-ray of the SI joints
- MRI of spine and SI joints (in a subset of subjects at selected sites)
- Assessment of SpondyloArthritis International Society criteria (ASAS)
- Patient's global assessment of disease activity (VAS)
- Patient's assessment of back pain intensity (VAS)
- Bath Ankylosing Spondylitis Functional Index (BASFI)
- Bath Ankylosing Spondylitis Disease Activity Index (BASDAI)
- hsCRP
- ASDAS-CRP and ASDAS response categories

All efficacy assessments should be performed prior to administration of study treatment. Details relating to the administration of all PROs are provided in [Appendix 6](#).

6.4.1 X-ray

X-rays will be obtained as defined in the schedule of assessments ([Table 6-1](#) and [Table 6-2](#)) and according to the imaging acquisition guidelines provided by the central imaging lab. Prior to the first imaging assessment for the study, the center should be trained and qualified by the central imaging lab. The X-ray requirements include lateral views of the cervical and thoracolumbar spine for mSASSS scoring (bottom 1/3 of C2 through top 1/3 of T1, inclusive) and antero-posterior view of the pelvis including visibility of both SI joints. These images should be transferred to the central imaging lab following acquisition. Some X-rays may need to be repeated if deemed unacceptable by central review. In case of insufficient quality, the site will be advised and trained on any quality issues prior to the repeat X-ray, to keep any repeat X-rays to a minimum. The central imaging lab will conduct independent review for all spine and SI X-rays in this study.

6.4.1.1 No radiographic progression in mSASSS

No radiographic progression in mSASSS is defined as a change from baseline in mSASSS at Week 104 of ≤ 0.5 . While the primary analyses will be based on this definition, additional analyses using ≤ 0 and < 2 will be performed.

6.4.1.2 Syndesmophyte

A syndesmophyte will be defined as a score of ≥ 2 for any individual vertebral edge within evaluable vertebral units. A new syndesmophyte is defined as an individual vertebral edge with a score of 0 or 1 at baseline that changes to a score of 2 or 3 at Week 104.

6.4.2 MRI

MRI will be performed at selected sites in a subgroup of approximately 30% of all randomized subjects. MRI will be performed to assess SI and spinal inflammation using a scoring system for quantification of AS-related pathologies, to investigate whether these changes are affected

by treatment with secukinumab or GP2017. The images will be obtained as defined in the schedule of assessments (Table 6-1 and Table 6-2) and according to the imaging acquisition guidelines provided by the central imaging lab. The MRI for each subject will include T1 and STIR sequences of the sagittal spine (cervical, thoracic and lumbar) and oblique coronal of the pelvis including both SI joints. These MRI images should be transferred as anonymized electronic files to the central imaging lab following acquisition. The central imaging lab will conduct independent review for all spine and SI MRI imaging in this study.

6.4.3 Assessment of SpondyloArthritis International Society criteria (ASAS)

The ASAS response measures consist of the following assessment domains (Sieper 2009).

ASAS domains:

- Patient's global assessment of disease activity measured on a VAS scale
- Patient's assessment of back pain, represented by either total or nocturnal pain scores, both measured on a VAS scale
- Function represented by BASFI average of 10 questions regarding ability to perform specific tasks as measured by VAS scale
- Inflammation represented by mean duration and severity of morning stiffness, represented by the average of the last 2 questions on the 6-question BASDAI as measured by VAS scale

